	To evaluate improvement or maintenance of Quality of Life parameters in patients with Alzheimer's Disease	Quality of life parameters to be assessed include (but are not limited to): • Alzheimer's Disease Cooperative Study Mild Cognitive Impairment Activities of Daily Living scale (ADCS-MCI-ADL24) • Depression Anxiety Stress Scale (DASS-21)	
	To assess the safety and tolerability of Lorelco TM in patients with Alzheimer's Disease	Safety and tolerability endpoints include: Incidence, type and severity of AEs Dose-limiting toxicities (DLTs) Changes from baseline in: electrocardiogram (ECG)	

Protocol Version 4, 06 OCT 2021

Confidential

Page 5 of 70

Curtin University	Study Protocol Protocol No.: PIA-2020
	parameters vital sign measurements body weight physical examination findings clinical laboratory parameters

Inclusion Criteria

Patients must satisfy all of the following criteria to be enrolled in the study:

- 1. Must have given written informed consent before any study-related activities are carried out and must be able to understand the full nature and purpose of the trial, including possible risks and adverse effects.
- 2. Adult males and females, 18 to 84 (inclusive) at screening.
- 3. Diagnosis of Alzheimer's Disease confirmed by:
 - a. A positive amyloid biomarker (PET scan) indicative of AD pathology,
 - b. Mini-mental-state examination (MMSE) score of 22 or greater,
 - Free and cued selective reminding test (FCSRT) cueing index of 0.79 or less OR free recall score ≤17
 - d. Clinical Dementia Rating (CDR) global score of 0.5 or 1.0.
- 4. Able to take oral medications and willing to record daily adherence to the study drug.
- 5. QT interval corrected using the Fridericia method (QTcF) ≤ 450 msec for males and ≤ 460 msec for females at screening and on Day 1, prior to dose administration (the mean of the two time points will be used to determine eligibility).
- 6. Evidence of adequate hepatic function at screening, as defined by the following:
 - a. Aspartate aminotransferase (AST) and alanine aminotransferase (ALT) \leq 2.5 × upper limit of normal (ULN)and
 - b. Total bilirubin $\leq 1.5 \times ULN$.
- 7. Evidence of adequate renal function, as defined by a calculated creatinine clearance ≥ 50 mL/min using the Cockcroft-Gault equation or 24-hour urine collection with plasma and urine creatinine concentrations respectively.

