4.4 Risk Assessment and Guidance for Investigators

Prolongation of the QT interval can occur in patients on probucol. Clinical trials by Yamashita¹⁰ and Kang¹¹ reported significantly more prolonged QT interval adverse events in individuals taking probucol (LorelcoTM), compared to controls. While drug-induced prolonged QT interval can be associated with significant adverse side effects such as ventricular arrhythmia (torsades de pointes), studies involving the use of 500 mg of Probucol daily, reported probucol-induced prolonged QT interval was not associated with, or increased the incidence of, ventricular arrhythmias. Furthermore, Walldius¹² reported that there was no significant difference in cardiovascular clinical events between individuals taking probucol and controls. No malignant arrhythmias or torsades de pointes were reported for either group. The absence of arrhythmias may be due to strict prolonged QT/QTc interval exclusion

Protocol Version 4, 06 OCT 2021

Confidential

Page 19 of 70

criteria. While there is no consensus on upper limit corrected QT/QTc interval values, many studies adopt an absolute QT/QTc interval prolongation of > 500ms. This reduces the risk of ventricular arrhythmia, as participants are discontinued prior to prolonged QT intervals associated with arrhythmia.

While QT prolongation by probucol may not enhance the occurrence of lethal ventricular arrhythmias, studies have identified several clinical risk factors for drug-induced arrhythmias, including probucol. These include;

- Cardiac factors (including congenital long QT syndrome, family history of sudden cardiac death, bradycardia)
- Myocardial hypertrophy
- Heart failure
- Liver disease
- Thyroid Dysfunction
- Renal or hepatic impairment

The above clinical risk factors should be considered prior to treatment with probucol¹³.

Further information regarding Lorelco $^{\text{TM}}$ is available in the Investigator's Brochure.

Protocol Version 4, 06 OCT 2021

Confidential

Page 20 of 70

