6.7 Dose Stopping Rules and Individual Dosage Adjustments

Dosing may be stopped or modified if suspected adverse drug reactions, changes in vital signs, ECGs, or clinical laboratory results are observed, and these changes pose a significant health risk. Of particular note for dose discontinuation are the following criteria;

- Corrected QT/QTc interval is in excess of 500 ms, or if it increases > 50 ms compared to baseline (baseline will be calculated as the mean of two time points, screening and baseline day 1).
- Occurrence of QT/QTc interval prolongation in association with symptoms of arrhythmia
- Subsequent prescription of a drug with potential QTc prolongation (Antimalarial; Macrolides; Quinolones; Triazole antifungals; Anti-arrhythmic; Antiemetic; Antidepressant; Antipsychotics)
- Evidence of Liver dysfunction, or primary biliary cirrhosis
- If for any reason the Investigator determines that continued participation in the trial is not in the participant's best interest.

The study may be terminated at any point in time at the discretion of the Sponsor.

Clinically or medically significant suspected adverse drug reactions, and SAEs considered to be related to study procedures will be followed until resolved or considered stable.

If an unscheduled interruption of treatment occurs, the PI should notify the Sponsor (via the Clinical Research Organization [CRO]) at the earliest possible time. A missed dose will not be made up. In the event that a patient requires an unscheduled interruption of treatment under conditions other than those associated with toxicity, the case will be reviewed by the PI and the MM, and discussed with the Sponsor/CRO to determine whether such a patient will be allowed to resume treatment.

At the discretion of the Investigator, a participant may be reinstated in the study 4 weeks after discontinuation of the participant. This will be evaluated on a case by case basis, and will also be reviewed by the DSMB. Participants will have a safety evaluation 4 weeks following study drug discontinuation.

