7.2 Inclusion Criteria

Patients must satisfy all of the following criteria to be enrolled in the study:

- 1. Must have given written informed consent before any study-related activities are carried out and must be able to understand the full nature and purpose of the trial, including possible risks and adverse effects.
- 2. Adult males and females, 18 to 84 (inclusive) at screening.
- 3. Diagnosis of Alzheimer's Disease confirmed by:
 - a. A positive amyloid biomarker (PET scan) indicative of AD pathology,
 - b. Mini-mental-state examination (MMSE) score of 22 or greater,
 - c. Free and cued selective reminding test (FCSRT) cueing index of 0.79 or less OR free recall score ≤17
 - d. Clinical Dementia Rating (CDR) global score of 0.5 or 1.0.
- 4. Able to take oral medications and willing to record daily adherence to the study drug.
- 5. QT interval corrected using the Fridericia method (QTcF) ≤ 450 msec for males and ≤ 460 msec for females at screening and on Day 1, prior to dose administration (the mean of two measurements will be used to determine eligibility).
- 6. Evidence of adequate hepatic function at screening, as defined by the following:
 - a. Aspartate aminotransferase (AST) and alanine aminotransferase (ALT) $\leq 2.5 \times$ upper limit

Protocol Version 4, 06 OCT 2021

Confidential

Page 28 of 70

of normal (ULN) (\leq 5 × ULN if liver metastases are present); and

- b. Total bilirubin ≤1.5 × ULN (< 2.0 x ULN for subjects with liver metastases or documented Gilbert's syndrome).
- 7. Evidence of adequate renal function, as defined by a calculated creatinine clearance ≥50 mL/min using the Cockcroft-Gault equation or 24-hour urine collection with plasma and urine creatinine concentrations respectively.
- 8. Adequate coagulation laboratory assessments (i.e. results within normal ranges, per local laboratory definition) at screening.
- 9. Lipids (total cholesterol, HDL and LDL) must be within < 1.5 x the upper limit of normal for the local laboratory reference range at the screening visit.
- 10. FBC must be within < 1.5 x the upper limit of normal for the local laboratory reference range at the screening visit.

11. Female volunteers:

- a. Must be of non-childbearing potential (i.e., surgically sterilised [hysterectomy, bilateral salpingectomy, bilateral oophorectomy at least 6 weeks before the screening visit]) or postmenopausal (where postmenopausal is defined as no menses for 12 months without an alternative medical cause, or

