11.5.3 Electrocardiogram

Twelve-lead ECGs will be assessed (including but not limited to the measurements of ventricular HR, PR interval, RR interval, QRS duration, QT interval and QTcF). Screening and prior to first dose, triplicate 12-lead ECGs (collected within 5 minutes with each reading separated by at least 1 minute) will be taken to establish eligibility at baseline. Triplicate ECGs will also be recorded at the EOT visit. The average value for the triplicate will be utilised for assessing QTcF inclusion criteria. All other ECGs will be single readings. However, if any of the ECG measurements is out of normal range, it will be repeated in triplicate (within 5 minutes, with each reading separated by at least 1 minute).

ECG normal ranges are as follows:

- PR interval: 120 msec 220 msec (inclusive);
- QRS duration: < 120 msec;
- QTcF \leq 450 msec (males); QTcF \leq 460 msec (females);
- HR 45-100 beats/min (inclusive)

If the "re-check" triplicate's average is still above these parameters, the PI shall be notified for a determination on further action. The same model of ECG machine should be used for Screening, pre-dose and post-dose readings for all patients. ECGs will be taken after at least 5 minutes in a supine quiet rest. ECGs will be interpreted, signed and dated by the PI, or medically qualified designee. The ECGs will be classified as normal, not having a clinically significant abnormality or having a clinically significant abnormality. In addition, ECG

Protocol Version 4, 06 OCT 2021

Confidential

Page 38 of 70

parameters of HR, PR interval, QT interval, PR interval, R-R interval, QRS duration, and QTcF will be noted on the eCRF.

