	Eligibility (including medical history, staging, and concomitant medication usage) to be reviewed, and eligibility confirmed prior to dose administration on Day 1.
--	---

- ² Concomitant medication usage to be reviewed by study staff at each scheduled visit and telephone call
- Full physical examination at Screening and End of Study visit to include, at a minimum, assessment of the following systems: skin, head, ears, eyes, nose and throat, lymph nodes, heart, chest, abdomen and extremities, and a neurological examination (assessment of speech, cranial nerves, motor power, deep tendon reflexes, sensation, coordination and gait), and any other focused assessments suggested by the presence of specific symptoms. All abnormal findings noted at the screening visit should be recorded as medical history.

All other physical examinations will be abbreviated on symptom directed at the discretion of the investigator

- Participants should be resting in a supine position for at least 5 minutes prior to and during vital signs measurements. Vital sign assessments may be repeated once, if abnormal values were recorded in the first instance, at the discretion of the PI.
- ECGs will be taken after at least 5 minutes in a supine quiet rest position. Screening and prior to first dose, triplicate 12-lead ECGs (within 5 minutes, with each reading separated by at least 1 minute) will be taken to establish baseline. The average value for the triplicate will be utilized for assessing QTcF inclusion criteria. Triplicate 12-lead ECGs will also be recorded at the EoS visit. All other post-first dose ECGs will be single readings. In case of evident bad quality (e.g. muscle tremor) of the tracing, the ECG will be repeated.
- For women of childbearing potential only. Testing must be performed, and confirmed negative (hCG \leq 5 U/L), prior to dose administration.
- For women of childbearing potential only. If the hCG blood test is > 5 U/L but < 25 U/L, repeat hCG test will be completed after 7 days.
- Patients are required to fast for a minimum of 8 hours prior to blood sample collection. Water is permitted. Fasting blood tests include serum thyroid, CRP, iron studies, B12, folate, blood sugar, HbA1c and lipids (refer to APPENDIX 5).

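### Inclusion 5 judges QTcF on the mean of screening and Day 1, so a low screening value can offset an over-limit pre-dose ECG

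*Protocol*

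**What the plan says.** - **Inclusion 5, section 7.2.** QTcF must be at most 450 ms (men) or 460 ms (women) "at screening and on Day 1, prior to dose administration (the mean of two measurements will be used to determine eligibility".
- **Inclusion 5, synopsis.** The limits are the same, and the averaged values are identified: "the mean of the two time points will be used to determine eligibility".
- **Section 11.5.3.** Triplicate ECGs are taken at screening and before the first dose: "The average value for the triplicate will be utilised for assessing QTcF inclusion criteria". Note 5 to the schedule (Appendix 1) says the same. Neither mentions a mean across visits.
- **Exclusion 2 (7.3 and synopsis).** A separate Bazett limit excludes QTcB above 450 ms (men) or 470 ms (women). It is not averaged, and no time point is named. Schedule note 1 wants "eligibility confirmed prior to dose administration on Day 1".
- **Out-of-range ECGs (11.5.3).** The normal range uses the same 450/460 ms QTcF limits. An out-of-range ECG is repeated in triplicate, and if the average is still over, "the PI shall be notified for a determination on further action".
- **Stopping rule (6.7).** Dosing stops for QTc above 500 ms or a rise of more than 50 ms, where "baseline will be calculated as the mean of two time points, screening and baseline day 1".
- **Timing.** Screening may be up to 56 days before Day 1 (synopsis, schedule, and the text with Figure 1; another paragraph of 6.1 says 24).

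**The concern.** The criterion names a limit at two time points and then decides on one number that neither time point has to meet. Nothing in the protocol expressly requires the pre-dose value to pass on its own once the mean passes. The ECG nearest to dosing can therefore be over the limit and be outvoted by a reading that is weeks old.

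This matters because QT prolongation is the risk with which section 4.4 opens, and that section relies on strict screening when it reads the earlier trials: "The absence of arrhythmias may be due to strict prolonged QT/QTc interval exclusion" criteria. The same section lists bradycardia among the risk factors for drug-induced arrhythmia, and low heart rate is where the Bazett limit is most lenient. What is at stake is safety screening. No sample size, power or type I error depends on it.

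**Working it through.** The plan gives no figure to reproduce. The inputs are the QTcF limits (7.2), the Bazett limits (7.3), the stopping thresholds and baseline (6.7), and the 5 ms manual measurement step (12.8).

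**1. Mean rule alone.** The largest pre-dose QTcF that passes is 2 × limit − screening QTcF. With a screening value of 430 ms this is 2 × 450 − 430 = 470 ms in men and 2 × 460 − 430 = 490 ms in women.

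**2. Adding Bazett at the pre-dose ECG.** QTcF = QT/RR^(1/3) and QTcB = QT/RR^(1/2), with RR = 60/HR, so QTcB = QTcF × RR^(−1/6). The ratio is 0.9701 at 50 bpm, 0.9856 at 55 and 1.000 at 60. A given QTcF passes Bazett up to HR = 60 × (Bazett limit / QTcF)^6:

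| Sex | Pre-dose QTcF (ms) | Passes Bazett up to (bpm) |
|---|---|---|
| Man | 455 | 56.2 |
| Man | 460 | 52.6 |
| Man | 470 | 46.2 |
| Woman | 461 | 67.4 |
| Woman | 465 | 64.0 |
| Woman | 470 | 60.0 |
| Woman | 490 | 46.7 |

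In men the two formulas share the 450 ms limit, so a gap exists only below 60 bpm. In women the Bazett limit is 10 ms higher, so values of about 460–470 ms pass at ordinary resting rates, up to about 67 bpm. The large exceedances of step 1 survive only at about 46 bpm or below.

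**3. Patients admitted under both rules**, each over the QTcF limit by more than the 5 ms measurement step:

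| Patient | Screening, pre-dose (ms) | HR | Mean | QTcB | Over limit | Stop in 6.7 | Distance from pre-dose value to stop |
|---|---|---|---|---|---|---|---|
| Man | 430, 460 | 50 | 445 | 460 × 0.9701 = 446.2 | 10 | 445 + 50 = 495 | 35 |
| Woman | 440, 468 | 60 | 454 | 468.0 | 8 | 504, capped at 500 | 32 |
| Woman | 440, 470 | 55 | 455 | 470 × 0.9856 = 463.2 | 10 | 505, capped at 500 | 30 |

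All three heart rates lie within the 45–100 bpm that 11.5.3 calls normal.

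**4. How often.** The protocol gives no QTc or heart-rate distribution, so the number affected cannot be derived. As an illustration only, assume independent normal visit values with SD 5, 8 or 12 ms around a patient's true QTcF. The chance of a pre-dose value over the limit with a passing mean, before Bazett or any re-check, is about 12.5% at each SD if the true value sits on the limit. If it sits 10 ms below, the chance is 2.1%, 8.1% and 12.3%. These are chances for borderline patients; the share of patients who are borderline is unknown.

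**5. Which ECG is Day 1?** Section 6.1 has patients randomised and then returning on Day 1, and the dosing table gives placebo to everyone in Weeks 1 and 2. Sections 11.8 and 12.8 list an ECG at baseline and another at Week 3. The schedule, as it can be read, marks an ECG at screening and at Week 3 Day 1 but none at Visit 0, and marks an eligibility check at all three. If Day 1 is in Week 1, two placebo weeks and a further ECG precede active drug. If it is Week 3 Day 1, active drug starts that day.

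**The case against.** **The averaging is deliberate.** It appears in two places, and the same mean is the baseline in 6.7. Averaging two visits dampens visit-to-visit variation, and in step 4 every patient's true value is at or below the limit. This stands as a reason to keep the mean as the baseline for change. It is weaker for eligibility: the triplicates already reduce noise within a visit, and the older reading says less about the patient about to be dosed.

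**11.5.3 may already require each visit to pass.** The triplicate average can be read as a per-visit test. It can equally be read as defining the value at each visit that then enters the mean. The text does not decide, so part of this point is an internal inconsistency rather than a settled loophole.

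**Other safeguards cover the rest.** Bazett removes most cases at ordinary heart rates. A persistently over-range ECG goes to the investigator, who may exclude on general grounds (end of 7.3) and is told in 4.4 to weigh bradycardia. The stops at 500 ms and above 50 ms apply, and the patients in step 3 reach a stop after a rise of 30–35 ms from their pre-dose value. These reduce the risk, but none makes the patient ineligible.

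**Stronger readings to avoid.** A reader might infer that patients 20 or 30 ms over the limit would routinely be dosed. That holds only if Bazett is ignored on Day 1, which schedule note 1 argues against, or at about 46 bpm and below. A reader might also infer damage to the efficacy comparison. Nothing supports that: the same rule applies to both arms.

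**Conclusion.** The point holds as a minor safety and consistency matter. As written in 7.2 and the synopsis, the mean rule can admit a patient whose pre-dose QTcF is over the stated limit, and 11.5.3 with schedule note 5 leaves open whether that is intended. If Bazett is applied to the pre-dose ECG, the remaining gap is men below 60 bpm, and women at about 460–470 ms up to about 67 bpm (above 470 ms, only below 60 bpm). The examples are 8–10 ms over. The number of patients is unknown and probably small.

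The conclusion assumes that the synopsis wording identifies the two averaged values and that note 1 brings Bazett to the pre-dose ECG. The placebo weeks cannot be counted on as a buffer until the protocol says which visit is Day 1.

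**What to change.** - Require the triplicate-mean QTcF to be at most 450 ms (men) or 460 ms (women) separately at screening and at the last ECG before dosing. Delete the averaging parenthesis.
- Use the same wording in the synopsis, 7.2, 11.5.3 and schedule note 5.
- State that the Bazett limit applies at the same two ECGs.
- Name the visit that is Day 1 and show its ECG in the schedule.
- Obtain the second ECG before randomisation where possible. Otherwise, patients who fail it are not dosed but stay in the all-randomised population that 13.6 uses for the primary analysis.
- The two-time-point mean may stay as the QTc baseline in 6.7.

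**Cost.** The triplicate ECGs are already required, so this is mainly amendment wording. A mean above the limit implies at least one value above it, so the new rule excludes everyone the present rule does and a few more. Some of the extra exclusions will reflect only visit-to-visit variation, including patients who were over at screening but within the limit before dosing. If the second ECG stays after randomisation, some will be post-randomisation exclusions from dosing rather than screen failures.

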- 8. Adequate coagulation laboratory assessments (i.e. results within normal ranges, per local laboratory definition) at screening.
- Lipids (total cholesterol, HDL and LDL) must be within < 1.5 x the upper limit of normal for the local laboratory reference range at the screening visit
- 10. FBC must be within < 1.5 x the upper limit of normal for the local laboratory reference range at the screening visit
- 11. Female volunteers:
 - a. Must be of non-childbearing potential (i.e., surgically sterilised [hysterectomy, bilateral salpingectomy, bilateral oophorectomy at least 6 weeks before the screening visit]) or postmenopausal (where postmenopausal is defined as no menses for 12 months without an alternative medical cause at the screening visit), or

Protocol Version 4, 06 OCT 2021

Confidential

Page 6 of 70

b. If of childbearing potential, must agree not to donate ova, not to attempt to become pregnant and, if engaging in sexual intercourse with a male partner, must agree to the use of acceptable forms of highly effective contraception (refer to Appendix 5) from the time of signing the consent form until at least 30 days after the last dose of the study drug.

12. Male volunteers:

- a. Engaging in any sexual intercourse, including those who are infertile and do not produce sperm (e.g. post-vasectomy), must abstain from unprotected sex until the End of Study visit or equivalent i.e. 4 days after last dose
- b. Must agree to abstain from sperm donation, and if engaging in sexual intercourse with a female of child bearing potential must agree to the use of an acceptable form of highly effective contraception (refer to Appendix 5) from the time of signing the consent form until at least 90 days after the last dose of study drug.
- 13. Have suitable venous access for blood sampling.
- 14. Be willing and able to comply with all study assessments and adhere to the protocol schedule and restrictions.
- 15. A study partner (partner/spouse/carer) consents to the minimum requirements:
 - a. will attend at least one screening visit
 - b. will be available via phone or in person to provide information to the study as required

Exclusion Criteria

A patient who meets any of the following exclusion criteria will not be eligible for inclusion in the study:

- Recorded number of falls in previous 12 months and during trial. Participants who report multiple falls with potential loss of consciousness will be excluded

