Patients will also undertake safety and other assessments as required on Days 1 (± 2 days) on Weeks 1, 2, 3, 4, 5, 15, 26, 39, 52, 65, 78 and 104.

A study design overview is shown in Figure 1.
Protocol Version 4, 06 OCT 2021 Confidential

Page 22 of 70

Curtin University Study Protocol
Protocol No.: PIA-2020

Figure 1. Study Design Overview

Patients will be screened between Day -56 to Day -1.

Safety and tolerability assessments will include vital signs, 12-lead ECGs, physical examinations, clinical laboratory tests (haematology, serum chemistry, coagulation, lipid analysis and urinalysis), and AE monitoring, as described in Section 11.8. Blood samples will be collected at specified times, as described in the schedule of assessments (APPENDIX 1).

Efficacy assessments include imaging using, PET scan and Magnetic Resonance Imaging (MRI) as described in Section 11.9. Imaging assessments will be performed at screening, and the 104 week visit or at last study visit if subject discontinues.

A final end of study visit will occur 4 weeks (\pm 2 weeks) following the last study drug administration.

There are no scheduled overnight confinement periods, however if patients experience any clinically significant adverse events (AEs) during the study, they may be admitted to the clinical facility for further observation at the discretion of the PI.

In the event of strong clinical benefit, and at the discretion of the study doctor, a participant may be reinstated in the study 4 weeks after discontinuation of the participant due to AE. This will be evaluated on a case by case basis.

Regardless of perceived benefit, participants cannot continue probucol at the end of the study as LorelcoTM is not approved for use in Australia. If strong clinical support is identified in the study, this will support effectiveness and phase III trials.

LorelcoTM will be evaluated at a single dose levels with dose increasing to BID by week 4 (Table 2). Thirty patients will initially be enrolled into single-patient cohorts and will be observed during the evaluation period (Week 2 Day 1 to Week 6).

If the patients do not experience any ≥Grade 2 AEs that are deemed related to study treatment, then additional patients may be dosed. The decision to commence dosing in additional patients will be at the discretion of the SRC following review of all AEs, clinical findings, laboratory results.

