- b. If of childbearing potential, must agree not to donate ova, not to attempt to become pregnant and, if engaging in sexual intercourse with a male partner, must agree to the use of acceptable forms of highly effective contraception (refer to Appendix 5) from the time of signing the consent form until at least 30 days after the last dose of the study drug.

12. Male volunteers:

- a. Engaging in any sexual intercourse, including those who are infertile and do not produce sperm (e.g. post-vasectomy), must abstain from unprotected sex until the End of Study visit or equivalent i.e. 4 days after last dose
- b. Must agree to abstain from sperm donation, and if engaging in sexual intercourse with a female of child bearing potential must agree to the use of an acceptable form of highly effective contraception (refer to Appendix 5) from the time of signing the consent form until at least 90 days after the last dose of study drug.
- 13. Estimated life expectancy of at least 2 years, in the opinion of the Investigator.
- 14. Have suitable venous access for blood sampling.
- 15. Be willing and able to comply with all study assessments and adhere to the protocol schedule and restrictions.
- 16. A study partner (partner/spouse/carer) consents to the minimum requirements:
 - a. will attend at least one screening visit
 - b. will be available via phone or in person to provide information to the study as required.

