10.4 Contraception

Female patients of child-bearing potential, with a fertile male sexual partner, should use highly effective methods of birth control (APPENDIX 6) from signing the consent form until at least 3 months following the last dose of study therapy.

Male patients, who are not surgically or biologically sterile, should use a condom in addition to having the female partner a use highly effective methods of birth control (APPENDIX 6) from signing the consent form until 3 months following the last dose of study therapy.

All study patients must be willing to ensure that corresponding sexual partners practice these same methods of highly effective birth control for the same duration.

Protocol Version 4, 06 OCT 2021

Confidential

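### Inclusion 11b ends women's contraception at a minimum of 30 days after the last dose, but section 10.4 says at least 3 months; inclusion 12a misdates the End of Study visit as 4 days after the last dose

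*Protocol*

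**What the plan says.** **Women.** Inclusion 11b appears in the synopsis and in section 7.2 with the same period. Women of childbearing potential must not donate ova or try to become pregnant, and with a male partner must use highly effective contraception, "from the time of signing the consent form until at least 30 days after the last dose of the study drug". Section 10.4 addresses women of childbearing potential who have a fertile male partner and asks for highly effective birth control "from signing the consent form until at least 3 months following the last dose of study therapy".

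**Men.** Inclusion 12a, again in both places, says that men having any intercourse, infertile men included, "must abstain from unprotected sex until the End of Study visit or equivalent i.e. 4 days after last dose". Inclusion 12b covers sperm donation, and contraception with partners of childbearing potential, "from the time of signing the consent form until at least 90 days after the last dose of study drug". Section 10.4 adds: "Male patients, who are not surgically or biologically sterile, should use a condom in addition to having the female partner" use a highly effective method, "from signing the consent form until 3 months following the last dose of study therapy".

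**Timing of the visit.** Section 6.1 states: "A final end of study visit will occur 4 weeks", with a window of ±2 weeks, after the last administration of study drug. Sections 6.3 and 6.8 also give 4 weeks, and Appendix 1 places the visit at Week 108 with a ±2-week window.

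**General undertaking.** Inclusion 15 in section 7.2 (14 in the synopsis) reads: "Be willing and able to comply with all study assessments and adhere to the protocol schedule and restrictions". The opening of section 10 says that compliance with its restrictions is assessed before first dosing and during the study.

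**The concern.** Entry criteria are where a participant's undertakings are fixed, so they should match the restrictions that the protocol later imposes. For women they do not: the criterion and the restriction start at the same point, consent, and cover the same precaution, but end at different times. For men, 12a gives its own end point a date that the rest of the protocol contradicts.

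What is at stake is possible fetal exposure after dosing stops and the accuracy of what participants are told. Section 11.4 places the last pregnancy test at the End of Study visit. After that visit, protection depends mainly on the undertaking given at entry, and that is where the shorter figure stands. No efficacy or safety analysis depends on either figure.

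**Working it through.** There is no sample size, power or alpha figure to reproduce. The check sets the texts side by side and takes differences in days after the last dose.

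**Inputs**

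| Rule | Place | Ends, days after last dose |
|---|---|---|
| Women, inclusion 11b | Synopsis, 7.2 | 30 (minimum) |
| Women with a fertile male partner | 10.4 | 3 months (minimum) |
| Men, 12a, as glossed | Synopsis, 7.2 | 4 |
| End of Study visit | 6.1, 6.3, 6.8, Appendix 1 | 28, window 14 to 42 |
| Men, 12b | Synopsis, 7.2 | 90 (minimum) |
| Men, contraception | 10.4 | 3 months |

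**Length of 3 months.** The shortest run is 1 February to 1 May in a non-leap year: 28 + 31 + 30 = 89 days. A longest run is 1 July to 1 October: 31 + 31 + 30 = 92 days. A convenient single value is 90.

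**Women.** The gap between the minimums is 89 − 30 = 59 to 92 − 30 = 62 days, or 90 − 30 = 60 with the single value.

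**Where the gap falls.** With 3 months taken as 90 days, the disputed interval runs from day 30 to day 90. If the last visit is on day 28, all 60 days come after it. If the visit is as late as day 42, then 42 − 30 = 12 days come before it and 90 − 42 = 48 after.

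**Men, the gloss in 12a.** The nominal difference is 28 − 4 = 24 days. Across the window it is 14 − 4 = 10 to 42 − 4 = 38 days. The protocol sometimes uses the EoS label for Week 104 (section 11.6.3 and the imaging note to Appendix 1), but Week 104 is the end of dosing, so that reading does not give 4 days either.

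**Men, 12b against 10.4.** 90 days against 89 to 92 agree within 2 days, so there is no conflict over the period for partner contraception.

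**Appendix references.** 11b and 12b send the reader to Appendix 5 for contraception methods, and 10.4 to Appendix 6. The protocol has four appendices, and the methods are in Appendix 3.

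**The case against.** The best defence is that a site following the whole protocol reaches the longer period. Both women's periods are floors, so meeting 10.4 also meets 11b. All inclusion criteria must be satisfied together, including the one on adherence to restrictions, and compliance with section 10 is checked. A reader might infer that a woman can properly enter on a 30-day undertaking alone; the documents do not support that. Nor do they show that participants were told 30 days, since the consent form is not available here. This defence stands as a limit on the harm, but it does not reconcile the two figures, and the disputed weeks lie largely beyond the last scheduled contact.

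It is also fair to say that the 4 days is probably a slip for 4 weeks. The operative term in 12a is the visit itself, which other sections date clearly. That makes it an easy correction, but the gloss still states the end of a restriction wrongly.

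A stronger reading is tempting for men: that 12a, even with the visit dated correctly, contradicts 10.4's condom rule by ending about two months sooner. The two rules differ in scope. 12a covers any intercourse and includes infertile men. 10.4 covers men who are not sterile, and asks for a condom alongside the female partner's method. Nothing in 12a limits 10.4, and the men's contraceptive criterion, 12b, already runs for 90 days. It remains true that 12b does not repeat the condom that 10.4 adds, which is at most a reason for a cross-reference.

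**Conclusion.** Two statements in the entry criteria are wrong as written. For women of childbearing potential with a fertile male partner, 11b and 10.4 set minimums about 60 days apart (59 to 62). For men, 12a dates the End of Study visit 24 days too early (10 to 38 across the visit window).

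The figures assume 3 months of 89 to 92 days and a visit at day 28 ±14. The text does not show which period was intended for women. The two women's rules overlap without being identical: 11b also covers ova donation and attempts at pregnancy, and 10.4 is confined to women with a fertile male partner.

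This is a minor point. Few participants in an Alzheimer's disease trial are likely to be affected, although entry is open from age 18, and no analysis or power figure changes.

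**What to change.** - **11b, synopsis and section 7.2:** replace the 30-day minimum with *at least 3 months (90 days)*, in line with 10.4. Since the intended period is not shown, this takes the longer one already in the protocol as the cautious choice. The sponsor should confirm whether the ova-donation and pregnancy-attempt terms in the same sentence are meant to follow it.
- **12a, both places:** change 4 days to *4 weeks*, or delete the gloss and let the End of Study visit define the end point.
- **12b:** at most, add a cross-reference to 10.4. No new condom obligation should be written into 12a. It would make mandatory what 10.4 only recommends, and would extend it beyond the female-partner setting.
- **11b, 12b and 10.4:** cite Appendix 3 for contraception methods.
- **Consent form:** check it for the same figures.

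The cost is a wording amendment and a consent-form check. Visits, data collection and analysis are unchanged.
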